5.3 Risks of Study Procedures

5.3.1 Risks Associated with Withdrawal of IS Medications

Participants in Cohorts A and B may be randomized to withdraw their cohort-defining IS medications around the time of the additional homologous vaccine dose. Withdrawal of IS medications could lead to disease exacerbation and flare. Participants will be evaluated for increases in disease activity during the Baseline/Week 0 visit prior to administration of the additional homologous vaccine dose.

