8.4.1.2 Visit Windows for Pediatric Stage 2 Rollover Participants

For participants rolling from Pediatric Stage 1 into Pediatric Stage 2, the visit windows are defined below:

- Total Screening Period:
 - Up to 28 days from the Stage 1 Study Follow-up Visit at which negative, suboptimal or low immune response to the previous COVID-19 vaccine was obtained until the S2 Baseline/Week 0 visit.
 - If the S2 Baseline/Week 0 visit cannot be conducted within 28 days of the qualifying Stage 1 Follow-up Visit noted above, the participant will return to the site for a full S2 Screening visit, as described in Section 8.4.2.3.2 Screening for Pediatric Stage 2 Rollover Participants.
 - S2 Screening Phone Visit: at least 7 days prior to administration of the alternative vaccine at S2 Baseline/Week 0.
 - See Section 8.4.2.3.2 Screening for Pediatric Stage 2 Rollover Participants for more details on the screening procedures for rollover participants
- S2 Baseline (S2 Week 0/Day 1)
 - See Section 8.2.4 Baseline (Week 0/Day 1) Visit for more details on the S2 Baseline/Week 0 visit activities.
- S2 Week 1: Vaccine Diary Review Phone Visit (Day 8 – Day 12)
- S2 Week 4: (+/- 1 week)
- S2 Week 12: (+/- 2 weeks)
- S2 Week 24: (+/- 2 weeks)
- S2 Week 36: (+/- 2 weeks)
- S2 Week 48 (End of Study): (+/- 2 weeks)

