8.4.4 Baseline (Week 0/Day 1) Visit

Eligible participants who meet all inclusion criteria and none of the exclusion criteria for Stage 2 will proceed with visits and assessments according to Section 20.1 Schedule of Events, [Table 21](#) (newly recruited participant) or [Table 22](#) (rollover participant). Eligible participants will be assessed for disease activity and SARS-CoV-2 infection at the S2 Baseline/Week 0 visit, prior to receipt of an alternative vaccine dose. Prior to administering the alternative vaccine dose at the Baseline visit, the site will confirm the participant meets vaccine eligibility per the criteria below:

- No increase to the permitted concomitant medications in participants in Cohorts D and E between S2 Screening and S2 Baseline/Week 0.
- No B-cell depletion infusions or changes in permitted concomitant medications in participants in Cohort E between allocation and S2 Baseline/Week 0.
- No clinically active disease (including myocarditis or pericarditis) at S2 Baseline/Week 0 resulting in an increase/addition of IS medications. For participants with MS, no suggestion of a MS relapse per the investigator.
- No active myocarditis or pericarditis based on review of clinical symptoms.
- No positive molecular COVID-19 test at S2 Baseline/Week 0.
- No increase in oral, intramuscular, or intravenous steroids within 14 days of S2 Baseline/Week 0.

If the vaccine cannot be administered at the S2 Baseline Week 0 visit, it must be administered during the following 2-3 days. Vaccine eligibility will be confirmed prior to administration of the vaccine. **Administration of the alternative vaccine dose must occur within 28 days of the S2 Screening visit (newly recruited participant) or 28 days of when the data used for screening were obtained (rollover participant).**

If a **newly recruited participant** is not eligible to receive the alternative vaccine dose at S2 Baseline Week 0, he/she will be terminated from the study (see Section 11.2 Participant Stopping Rules and Withdrawal Criteria), and the participant will be replaced. If a **rollover participant** is not eligible to receive the alternative vaccine dose at S2 Baseline Week 0, he/she will continue on the previous Schedule of Events.

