^jParticipants in Cohort B (MTX) randomized to the withhold IS treatment plan will withhold their MTX for at least 7 days prior to and at least 7 days after receipt of an additional homologous vaccine dose at Baseline (not to exceed 21 days holding MTX). The site will call the participant prior to Baseline to remind the participant to withhold his/her MTX and after Baseline to remind the participant to restart his/her MTX.

^kParticipants in Cohort A (MMF/MPA) randomized to the withhold IS treatment plan will withhold their MMF/MPA for 3 days prior to and 10 days after receipt of an additional homologous vaccine dose at Baseline. The site will call the participant prior to Baseline to remind the participant to withhold his/her MMF/MPA and after Baseline to remind the participant to restart his/her MMF/MPA.

^lThe vaccine diary will be completed for 7 days after the additional homologous vaccine dose.

^mThe H-SLEDAI and PGA will be collected at Screening for all SLE participants to assess disease activity. The Tender/Swollen Joint Count and PtGA will be collected at Screening for all RA participants to assess disease activity using DAS28-CRP.

ⁿIf the Baseline/Week 0 visit occurs less than 10 days from the Screening visit, the following disease activity assessments do not need to be repeated: H-SLEDAI, DAS28-CRP, and PDAI.

^oThe EDSS will be collected whenever a MS relapse is suspected, and if applicable, at the time of relapse recovery (to occur 8-12 weeks after the suspected relapse EDSS assessment).

^pFor women of childbearing potential, a stat urine HCG prior to vaccination will be performed locally with point of care testing.

^qIf a participant is on a CD20 depleting agent, CD19+ B cells will be collected.

^rAntibody levels will be tested at each time point to test for IgG and IgM responses against SARS-CoV-2 spike, receptor binding domain, and nucleocapsid proteins.

^sCohort A (MMF/MPA) participants who are randomized to the Continue IS treatment arm will hold their morning dose of MMF/MPA until after the serum blood draw.

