ⁱParticipants in Cohort E (MTX) and participants in Cohort F (BCDT) who are also taking MTX will withhold their immunosuppressive medication for at least 7 days prior to and at least 7 days after receipt of the alternative vaccine dose at Stage 2 Baseline (not to exceed 21 days withholding of MTX). If necessary, the site will call the participant between Stage 2 Screening and Stage 2 Baseline to remind the participant to withhold his/her MTX. The site will call the participant after Stage 2 Baseline to remind the participant to restart his/her MTX.

^jParticipants in Cohort D (MMF/MPA) and participants in Cohort F (BCDT) who are also taking MMF/MPA will withhold their immunosuppressive medication for 3 days prior to and 10 days after receipt of the alternative vaccine dose at Stage 2 Baseline. If necessary, the site will call the participant between Stage 2 Screening and Stage 2 Baseline to remind the participant to withhold his/her MMF/MPA. The site will call the participant after Stage 2 Baseline to remind the participant to restart his/her MMF/MPA.

^kThe vaccine diary will be completed for 7 days after the alternative vaccine dose.

^lThe H-SLEDAI and PGA will be collected at Stage 2 Screening for all SLE participants to assess disease activity. The Tender/Swollen Joint Count and PtGA at Stage 2 Screening will be collected for all RA participants to assess disease activity using DAS28-CRP.

^mIf the Stage 2 Baseline/Stage 2 Week 0 visit occurs less than 10 days from the Screening visit, the following disease activity assessments do not need to be repeated: H-SLEDAI, DAS28-CRP, and PDAI.

ⁿThe EDSS will be collected whenever a MS relapse is suspected, and if applicable, at the time of relapse recovery (to occur 8-12 weeks after the suspected relapse EDSS assessment).

^oFor women of childbearing potential. Stat urine HCG prior to vaccination may be performed locally with point of care testing.

^pIf a participant is on a CD20 depleting agent, CD19+ B cells will be collected.

^qAntibody levels will be tested at each time point to test for IgG and IgM responses against SARS-CoV-2 spike, receptor binding domain, and nucleocapsid proteins.

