^HSAEs, MAAEs, NOCMCs, AESIs, COVID-19 diagnoses, and flares of a secondary autoimmune disease will be collected from Day 1 through the end of the participant's study participation.

^IEligibility confirmed by CDC card or documentation in medical records and results of response to initial COVID-19 vaccine regimen assessed by Elecsys® Anti-SARS-CoV-2 S (RBD) assay.

^JRandomization for Cohorts A and B must occur within 21 days of Screening and at least 7 days prior to Week 0/Day 1. During the randomization visit, sites will call participants to confirm medical history and concomitant medication data still meet eligibility criteria. Participants in Cohort C will not be randomized. These participants must have study eligibility confirmed and have the Baseline/Week 0 visit occur within 28 days of Screening.

^KParticipants in Cohort B (MTX) randomized to the withhold IS treatment plan will withhold their MTX for at least 7 days prior to and at least 7 days after receipt of vaccine booster at Baseline (not to exceed 21 days holding MTX). The site will call the participant prior to Baseline to remind the participant to withhold his/her MTX and after Baseline to remind the participant to restart his/her MTX.

^LParticipants in Cohort A (MMF/MPA) randomized to the withhold IS treatment plan will withhold their MMF/MPA for 3 days prior to and 10 days after receipt of vaccine booster at Baseline. The site will call the participant prior to Baseline to remind the participant to withhold his/her MMF/MPA and after Baseline to remind the participant to restart his/her MMF/MPA.

^MThe vaccine diary will be completed for 7 days after vaccine booster. If the participant consents to an optional mechanistic specimen collection at Week 1, the site will complete the review of the vaccine reaction diary prior to collecting specimens.

^NThe Tender/Swollen Joint Count, PGA, and PtGA at Screening will be collected for all JIA participants to assess disease activity using JADAS-10. The PGA and the SLEDAI-2K will be collected for pediatric SLE participants at screening for evaluation of the childhood-onset SLE criteria of global flare.

^OIf the Baseline/Week 0 visit occurs less than 10 days from the Screening visit, the following disease activity assessments do not need to be repeated: SLEDAI-2K, Tender/Swollen Joint count, CMAS, and physician-assessed relapse for MS.

^PThe PASI will only be assessed if a JIA participant has psoriatic arthritis.

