^jParticipants in Cohort D (MMF/MPA) and participants in Cohort F (BCDT) who are also taking MMF/MPA will withhold their IS medication for 3 days prior to and 10 days after receipt of the alternative vaccine dose at Stage 2 Baseline Week 0. If necessary, the site will call the participant between Stage 2 Screening and Stage 2 Baseline Week 0 to remind the participant to withhold his/her MMF/MPA. The site will call the participant after S2 Baseline Week 0 to remind the participant to restart his/her MMF/MPA.

^kThe vaccine diary will be completed for 7 days after vaccine booster. If the participant consents to an optional mechanistic specimen collection at Week 1, he site will complete the review of the vaccine reaction diary prior to collecting specimens.

^lThe Tender/Swollen Joint Count, PGA, and PtGA at Screening will be collected for all JIA participants in order to assess disease activity using JADAS-10. The PGA and the SLEDAI-2K will be collected for pediatric SLE participants at screening for evaluation of the childhood-onset SLE criteria of global flare.

^mIf the Baseline/Week 0 visit occurs less than 10 days from the Screening visit, the following disease activity assessments do not need to be repeated: SLEDAI-2K, Tender/Swollen Joint count, CMAS, and physician-assessed relapse for MS.

ⁿThe PASI will only be assessed if a JIA participant has psoriatic arthritis.

^oThe PASI will be assessed post-Baseline if a psoriatic arthritis flare is suspected.

^pThe CMAS is required for JDM participants 6 -17 years of age. The CMAS is optional for JDM participants who are 2-5 years of age.

^qThe EDSS will be collected whenever a POMS relapse is suspected, and if applicable, at the time of relapse recovery (to occur 8-12 weeks after the suspected relapse EDSS assessment)

^rFor postmenarcheal females only. Stat urine HCG prior to vaccination may be performed locally with point of care testing.

^sIf the S2 Screening visit occurs onsite, the molecular COVID-19 test and urine pregnancy test will be conducted. If Stage 1 or Stage 2 visit data is being used to assess Stage 2 eligibility and screening, the molecular COVID-19 test and urine pregnancy tests will be conducted at the S2 Baseline visit only.

^tIf a participant is on a CD20 depleting agent, CD19+ B cells will be collected.

^uAntibody levels will be tested at each time point to test for IgG and IgM responses against SARS-CoV-2 spike, receptor binding domain, and nucleocapsid proteins

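### Pediatric Stage 2 rollover (Table 22): a footnote lets four Week 0 disease-activity scores be replaced by scores up to 28 days old

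*Protocol*

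**What the plan says.** **The waiver.** In Table 22, mark M sits on four S2 Week 0 rows: SLEDAI-2K, tender/swollen joint count, CMAS and physician-assessed relapse. Footnote m says that if the "Baseline/Week 0 visit occurs less than 10 days from the Screening visit, the following disease activity assessments do not need to be repeated", and it then names these four items.

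**Screening for pediatric rollovers.** Section 8.4.1.2 has the entry "S2 Screening Phone Visit: at least 7 days prior to administration of the alternative vaccine at S2 Baseline/Week 0". It also allows at most 28 days from the qualifying Stage 1 follow-up visit to S2 Baseline. Section 8.4.2.3.2 lets screening be completed by telephone alone when the needed data exist from the last Stage 1 visit. Table 22 footnote d takes remotely screened values from the most recent follow-up visit, provided it was within the past 21 days. The only screening column in Table 22 is the phone visit.

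**Week 0 in the body text.** Section 8.4.4 states: "Eligible participants will be assessed for disease activity and SARS-CoV-2 infection at the S2 Baseline/Week 0 visit, prior to receipt" of the alternative dose. It gives no exception. It also requires confirmation that there is no clinically active disease leading to more immunosuppression and, for MS, no suggestion of relapse.

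**Drug hold.** Section 7.1.1 has MMF/MPA withheld from 3 days before the dose and MTX from at least 7 days before. In Stage 2 this applies to all of Cohorts D and E, and to Cohort F participants who also take these drugs.

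**Other schedules.** Tables 17, 18, 20 and 21 carry a similar waiver; in adult Tables 17 and 18 the listed items "do not need to be repeated: H-SLEDAI, DAS28-CRP, and PDAI". Adult rollover Table 19 carries none.

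**The concern.** A short-interval waiver makes sense when the participant was scored in person a few days earlier. In a remotely screened rollover, the event that starts the 10-day clock may be a telephone call at which no score was taken. The value then standing as Week 0 comes from a previous follow-up visit.

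Change in SLEDAI-2K, JADAS10 and CMAS, and physician-assessed relapse in POMS, are secondary endpoints (Section 3.3). Whether disease activity rises after the alternative dose is a Stage 2 secondary objective (Section 2.2.2). If one child's baseline is a fresh on-hold score and another's is an older pre-hold score, and only the appointment date decides which, change from Week 0 does not mean the same thing in both.

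**Working it through.** No figure in the plan needs reproducing; this is a count of days. Vaccination is day 0 and is taken to be given at the Baseline visit.

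**When the waiver can apply.** Screening is at least 7 days before vaccination (Section 8.4.1.2), and the waiver needs fewer than 10 days (footnote m). The call must therefore fall on day −9, −8 or −7. Table 22 allows day −21 to day −7, which is 15 days, so the waiver covers 3 of 15 permitted days.

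**Age of the carried-forward score.** Age = days from follow-up visit to call (0 to 21, footnote d) + days from call to vaccination (7 to 9), capped at 28 (Sections 8.4.1.2 and 8.4.4).

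| Call on day | Longest age before cap | After 28-day cap | Days from call to MMF/MPA hold (day −3) | Days from call to MTX hold (day −7, the minimum) |
|---|---|---|---|---|
| −7 | 21 + 7 = 28 | 28 | 7 − 3 = 4 | 7 − 7 = 0 |
| −8 | 21 + 8 = 29 | 28 | 8 − 3 = 5 | 8 − 7 = 1 |
| −9 | 21 + 9 = 30 | 28 | 9 − 3 = 6 | 9 − 7 = 2 |

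The shortest age is 0 + 7 = 7 days, so the range is 7 to 28 days. Table 22 footnote v words the limit differently, as 28 days from the Screening visit rather than from the data; on that wording alone the maximum would be 30.

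**Position relative to the hold.** The score is taken on or before the day of the call, and the hold starts on or after it. Section 8.4.3 has the hold explained during the Screening call, so a longer MTX hold would not start before the call either. When the waiver is used, none of the four items is scored between the start of the hold and vaccination.

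**Second reading.** If *Screening visit* means the visit at which the scores were obtained, they are 7 to 9 days old at vaccination. The age problem disappears, but the scores still do not post-date the start of the hold.

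**Consistency within Table 22.** The SLE global-flare row stays scheduled at Week 0 without the waiver mark. Footnote l ties SLEDAI-2K and PGA to that evaluation, yet the Week 0 SLEDAI-2K may be absent.

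**SAP.** It defers assessment windows (Section 8.1.2) and the JADAS-10, SLEDAI-2K, CMAS and POMS relapse analyses (Sections 8.3.7.6, 8.3.7.8, 8.3.7.9 and 8.3.7.11). It was written to Protocol version 3.0, before pediatric Stage 2 was added. Nothing there settles which value is baseline.

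**The case against.** **The check is not lost as a whole.** A reader might infer that children are vaccinated without any look at disease activity. The documents do not support that. Still scheduled at Week 0 without the waiver mark are the targeted and neurological exams, PGA, PtGA, the ACR global-flare criteria, the JDM flare assessment, PASI, EDSS, and the safety and disease-specific laboratory tests. Section 8.4.4 still requires eligibility confirmation, Section 6.7 bars vaccination during a flare at Baseline, and footnote v places all Week 0 assessments before the dose. The waiver is also permissive. This objection stands and limits the point to four named items.

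**Section 8.4.4 names no instrument.** It requires disease activity to be assessed and refers to the schedule for the visits and assessments. The conflict is therefore a poor fit between body text and footnote, not a flat contradiction. Section 5.3.1 says "Participants will be evaluated for increases in disease activity during the Baseline/Week 0 visit prior to administration", and a reader might add it as a second conflict. That section concerns Cohorts A and B before the homologous dose, so it does not reach the Table 22 population.

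**The term is ambiguous.** Section 8.4.1.2 separates the phone visit from a full Screening visit, and *repeated* suggests a score was taken at that visit. Against this, Section 8.4.2.3.2 speaks of a Screening visit conducted by phone. The phone reading is the better supported, but not the only one.

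**Frequency and attribution.** The documents give no booking pattern, so 3 of 15 permitted days is not a rate. A reader might also think that an on-hold baseline would separate hold effects from vaccine effects. It would not: the hold runs for 10 days (MMF/MPA) or at least 7 days (MTX) after the dose, so the two stay confounded.

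**The Table 19 comparison is partial.** It schedules no physician-assessed MS relapse at Week 0, so it is a precedent for leaving activity scores unwaived, not for the relapse item.

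**Conclusion.** The point holds in a limited form. On the reading in which the phone call is the Screening visit, footnote m lets four scores stand as S2 Week 0 values when they are 7 to 28 days old and were taken no later than the start of any hold. On the other reading they are 7 to 9 days old, and the hold statement is unchanged. The calculation assumes vaccination at the Baseline visit and the 28-day limit of Sections 8.4.1.2 and 8.4.4.

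The loss is confined to SLEDAI-2K, joint count, CMAS and physician-assessed relapse, and to children whose Screening falls on day −9 to −7. The primary antibody endpoint is untouched, and the affected endpoints are secondary and summarised descriptively. What remains is a baseline whose age and hold status depend on booking, a footnote that does not fit Section 8.4.4, and a global-flare row that may lack a current SLEDAI-2K. It should be corrected.

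**What to change.** Reconcile Table 22 footnotes d and m with Sections 8.4.1.2, 8.4.2.3.2 and 8.4.4. The cleaner route is to delete footnote m from Table 22, so that the four items are scored at S2 Week 0 in every pediatric rollover. The lesser route is to count the 10 days from the in-person visit at which the scores were obtained. That caps their age at 9 days but still leaves some baselines pre-hold and others on-hold. Whichever is chosen, the SAP should state which value is the baseline for these instruments.

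Do not make the waiver in Tables 18, 20 and 21 depend on whether a drug is being withheld. In Table 20 that would make baseline scoring differ between the randomised continue and withhold arms; any change there should apply equally to both.

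The cost is a footnote edit and, for the children concerned, repeating a short score at a visit that already takes place in person.

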20.2 CoFAR Grading Scale for Systemic Allergic Reactions Version 3.0

Grade 1	Grade 2	Grade 3	Grade 4	Grade 5
Reaction involving one of the following organ systems in which the symptoms are mild: Cutaneous Generalized pruritus, generalized urticaria, flushing, angioedema Upper respiratory Rhinitis, cough unrelated to laryngeal edema or bronchospasm Conjunctival Injection/redness, itching, tearing GI Nausea, abdominal pain (no change in activity level), single episode of vomiting and/or single episode of diarrhea	Reaction involving two or more of the following organ systems in which the symptoms are mild: Cutaneous Upper respiratory Conjunctival GI OR Reaction involving at least one of the following organ systems in which the symptoms are moderate:	Reaction involving one or more of the following organ systems: Lower respiratory Throat tightness, wheezing, chest tightness, dyspnea, cough that respond to short-acting bronchodilator treatment (including IM epinephrine) with or without supplemental oxygen GI Severe abdominal pain, more than two episodes of vomiting and/or diarrhea	Life-threatening reaction involving one or more of the following organ systems with or without other symptoms listed in Grades 1 to 3: Lower respiratory Throat tightness with stridor, wheezing, chest tightness, dyspnea, or cough associated with a requirement for supplemental oxygen and refractoriness to short-acting bronchodilator treatment (including IM epinephrine) ¹ OR Respiratory compromise requiring mechanical support Cardiovascular Reduced BP with associated symptoms of end-organ dysfunction (e.g., hypotonia [collapse], syncope) defined as: 
• Children: low systolic BP (age specific²) or	Death

Grade 1	Grade 2	Grade 3	Grade 4	Grade 5
	
Cutaneous
 
Generalized pruritus, generalized urticaria, flushing, angioedema
 
Upper respiratory
 
Rhinitis, cough unrelated to laryngeal edema or bronchospasm
 
Conjunctival
 
Injection/redness, itching, tearing
 
GI
 
Nausea, abdominal pain (with change in activity level), two episodes of vomiting and/or diarrhea
		
>30% decrease in systolic BP
 
 Adults: systolic BP of less than 90 mmHg or >30% decrease from baseline 	

1. Examples of refractoriness could include continuous albuterol nebulizer or epinephrine IV infusion or more than three IM epinephrine injections.
2. Low systolic BP for children is defined as: less than 70 mmHg from 1 month to 1 year of age, less than $(70 \text{ mmHg} + [2 \times \text{age}])$ from 1 to 10 years of age, and less than 90 mmHg from 11 to 17 years of age.

